9.4 Immunogenicity analysis

9.4.1 General approach

For the statistical analysis of immunogenicity endpoints, data from enrolled participants will be used according to the initial randomization assignment regardless of how many injections they received. Additional analyses may be performed, limited to participants who received all scheduled injections per protocol. Assay results that are unreliable, from specimens collected outside of the visit window, or from HIV-infected participants postinfection are excluded. Since the exact date of HIV infection is unknown, any assay data from blood draws 4 weeks prior to an infected participant's last seronegative sample and thereafter may be excluded. If an HIV-infected participant does not have a seronegative sample postenrollment, then all data from that participant may be excluded from the analysis.

Data from placebo arms will be pooled across groups ($n = 8$ for analysis in Part B). For analyses of immunogenicity after the second vaccination, data on the 3M-052-AF from Part A (with the maximum tolerated dose of the 3M-052-AF) and Part B will be pooled. Otherwise, analyses of immunogenicity will be performed separately for Part A and Part B participants.

Discrete categorical assay endpoints (e.g., response rates) will be analyzed by tabulating the frequency of positive response for each assay by antigen and treatment arm at each timepoint for which an assessment is performed. Crude response rates will be presented with their corresponding 95% confidence interval estimates calculated using the score test method [1]. Because of the small numbers of control participants in each group, no adjustment will be made to the vaccine arm estimates for the false positive rates (FPRs) in the control arms. Barnard's test will be used to compare the response rates of any 2 vaccine arms, with a significant difference declared if the 2-sided p-value is ≤ 0.05 .

For quantitative assay data (e.g., percentage of positive cells from ICS assay), graphical and tabular summaries of the distributions by antigen, treatment arm, and timepoint will be made. For all primary and secondary immunogenicity endpoints, box plots and plots of estimated reverse cumulative distribution curves (CDFs) will be used for graphical display of all of the study arms. Typically, the results will be shown for each vaccine arm and for the pooled placebo group.

The difference between arms at a specific timepoint will be tested with a nonparametric Wilcoxon rank sum test if the data are not normally distributed and with a 2-sample t-test if the data appear to be normally distributed. Individual tests comparing the 6 pairs of vaccine arms will be performed unless prespecified. If rank-based tests are used, then the tests will be inverted to construct Hodges-Lehmann point estimates and 2-sided $(1 - 0.05/6) \times 100\%$ confidence intervals (CIs) about the differences in location centers of the 6 pair-wise comparisons of vaccine arms. If actual-value tests are used then the Dunnett's procedure will be used to construct simultaneous confidence intervals about the pairs of mean differences for the many-to-one comparisons [2] when multiple vaccine arms are each compared with the pooled placebo group. Given that all pair-wise comparisons between the multiple vaccine arms are of interest, the Tukey procedure [3] will be used. An appropriate data transformation (e.g., \log_{10} transformation) may be applied to better

satisfy assumptions of symmetry and homoscedasticity (constant variance). Significance of the differences between pairs will be evaluated using two procedures, first based on whether the simultaneous 95% CIs exclude zero and secondly based on whether the nominal (unadjusted) 95% CIs exclude zero.

Scatterplots will be used to visualize the association between quantitative immune responses at Month 2.5 and prime interval, and between quantitative immune responses at Month 6.5 and both prime and boost interval variables in Part A.

Some immunologic assays have underlying continuous or count-type readout that are dichotomized into responder/nonresponder categories (e.g., intracellular cytokine staining). If treatment arm differences for these assays are best summarized by a mixture model, then either Lachenbruch's test statistic [4] or an alternative two-part test [5] will be used to evaluate the composite null hypothesis of equal response rates in the 2 arms and equal response distributions. Lachenbruch's test statistic equals the square of a binomial Z-statistic for comparing the response rates plus the square of a Wilcoxon statistic for comparing the response distributions in the subgroup of responders. A permutation procedure is used to obtain a 2-sided p-value. For estimation, differences in response rates between arms will be estimated using the methods described above, and in the subgroup of positive responders, differences in location parameters between arms will be estimated using the methods described above.

More sophisticated analyses employing repeated measures methodology (for example, linear mixed models or marginal mean models fit by generalized estimating equations) will be utilized to incorporate immune responses over several timepoints and to test for differences over time and differences in trajectories across treatment arms. For example, repeated measures analyses will be conducted to evaluate trajectories in innate immune response over Days 1, 3, 7 relative to responses measured at Day 0. However, inference from such analyses would be limited by the small sample size of this study. All statistical tests will be 2-sided and will be considered statistically significant if $p \leq 0.05$.

Based upon previous HVTN trials, missing 10% of immunogenicity results for a specific assay is common due to study participants terminating from the study early, problems in shipping specimens, or low cell viability of processed PBMCs. To achieve unbiased statistical estimation and inferences with standard methods applied in a complete-case manner (only including participants with observed data in the analysis), missing data need to be missing completely at random (MCAR). Following the most commonly used definition, MCAR assumes that the probability of an observation being missing does not depend on any participant characteristics (observed or unobserved). When missing data are minimal (specifically if no more than 20% of participants are missing any values), then standard complete-case methods will be used, because violations of the MCAR assumption will have little impact on the estimates and hypothesis tests.

If a substantial amount of immunogenicity data are missing for an endpoint (at least 1 value missing from more than 20% of participants), then using the methods that require the MCAR assumption may give misleading results. In this situation, analyses of the immunogenicity endpoints at a specific timepoint will be performed using generalized linear models fit by maximum likelihood. These methods provide unbiased estimation and inferences under the parametric modeling assumptions and the assumption that the missing data are missing at random (MAR). MAR assumes that the probability of an observation being missing may depend upon the observed responses and upon observed covariates, but not upon any unobserved factors. Generalized linear models for response

rates will use a binomial error distribution and for quantitative endpoints, a normal error distribution. For evaluating repeated immunogenicity measurements over time, linear mixed effects model will be used. If the immunological outcomes are left- and/or right-censored, then the linear mixed effects models of Hughes [6] will be used, because they accommodate the censoring. In addition, secondary analyses of repeated immunogenicity measurements may be done using weighted generalized estimating equation (GEE) [7] methods, which are valid under MAR. All of the models described above in this paragraph will include as covariates all available baseline predictors of the missing outcomes.

Some immunogenicity endpoints are only measured in subset of participants. For example, fine needle lymph node aspirates, bone marrow aspirates, and leukapheresis will be performed on consenting participants at a subset of sites, and immunogenicity endpoints based on these samples will only exist for participants enrolled at those sites. For such endpoints, exploratory analyses will be conducted to assess the correlation of participant characteristics measured in (nearly) all participants with the resource-intensive endpoints. For example, if the same assay is performed on blood and fine needle lymph node aspirate samples, then a scatterplot and Spearman rank correlation coefficient (r) will be used to assess the correlation of responses. If at least moderate correlations exist (eg, $r \geq 0.3$), then the semiparametric efficient analysis method of Rotnitzky and Robins [8] will be used (described in Gilbert, Sato et al. for application to vaccine studies [9]) to estimate the mean of the resource-intensive endpoint for each group and to compare means between groups.

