3.2 Objectives and endpoints for Part B

3.2.1 Primary objectives and endpoints for Part B

Primary objective 1:

To evaluate the safety and tolerability of intramuscular (IM) administration of BG505 SOSIP.664 gp140 with the following adjuvants: CpG 1018 + Alum, 3M-052-AF + Alum, GLA-LSQ, or Alum alone

Primary endpoint 1:

Signs and symptoms of local and systemic reactogenicity, laboratory measures of safety, adverse events (AEs), expedited AEs, and AEs of special interest (AESIs)

Primary objective 2:

To evaluate and compare the neutralizing antibody response induced by BG505 SOSIP.664 gp140 with different adjuvants (CpG 1018 + Alum, 3M-052-AF + Alum, GLA-LSQ, or Alum alone)

Primary endpoint 2:

Response rate and magnitude of serum antibody neutralization of autologous (HIV-1 BG505) and other heterologous Tier 2 HIV-1 strains as measured by TZM-bl assay 2 weeks after the second and third vaccinations

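### Section 9.4.1 gives the magnitude half of Part B primary endpoint 2 both an adjusted and a nominal reading over the six adjuvant pairs, but gives the response-rate half only an unadjusted one

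*SAP*

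**What the plan says.** **The endpoint.** SAP section 3.2.1 sets primary objective 2 of Part B as "To evaluate and compare the neutralizing antibody response induced by BG505 SOSIP.664 gp140 with different adjuvants". The four arms are CpG 1018 + Alum, 3M-052-AF + Alum, GLA-LSQ and Alum alone. Primary endpoint 2 is "Response rate and magnitude of serum antibody neutralization of autologous (HIV-1 BG505) and other heterologous Tier 2 HIV-1 strains", measured two weeks after the second and third vaccinations.

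**Response rates.** Section 9.4.1 states that Barnard's "test will be used to compare the response rates of any 2 vaccine arms, with a significant difference declared if the 2-sided p-value" is at most 0.05. Nothing is said about the number of pairs.

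**Magnitude.** The same section states: "Individual tests comparing the 6 pairs of vaccine arms will be performed unless prespecified". If rank tests are used, it asks for Hodges-Lehmann estimates with two-sided (1 − 0.05/6) × 100% "confidence intervals (CIs) about the differences in location centers of the 6 pair-wise comparisons of vaccine arms". If actual-value tests are used, it applies the Tukey procedure to the pairs. Significance is then read in two ways, "first based on whether the simultaneous 95% CIs exclude zero and secondly based on whether the nominal (unadjusted) 95% CIs exclude zero".

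**General policy.** Section 9 says that no formal adjustment is made for multiple safety endpoints, multiple primary immunogenicity endpoints or secondary endpoints. It allows adjustment within certain assays, for example over peptide pools.

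**The concern.** The six adjuvant pairs are the same family in both halves of one primary endpoint. For magnitude, the SAP recognises that family and gives the reader a simultaneous result before the nominal one. For response rates, the reader gets only a nominal result, worded as a declared significant difference, and cannot see whether it would survive the six comparisons. No reason is given for the difference.

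Part B is labelled an adjuvant comparison in the schema. Section 9.5.2 allows early unblinded reports to go to those who need them for future trial-related decisions. A rate difference that reaches 0.05 only because six pairs were examined could enter those discussions without a caveat.

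**Working it through.** **Inputs from the SAP.** Four arms, so 4 × 3 / 2 = 6 pairs. Evaluable n = 18 per arm at Months 2.5 and 6.5, from 20 enrolled and 10% missing (section 8.3). Barnard's test, two-sided, 0.05 per pair (section 9.4.1).

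**Step 1: the plan's own figure.** Section 8.3 states 97% power for 50% vs 100% using Fisher's exact test at two-sided 0.05. Full enumeration at 18 per arm gives 98.5%, and the normal approximation gives 96.7%. Both are within 2 points of the stated value. The Table 5 rates match a continuity-corrected formula within 1 point. These powers are per pair, with no allowance for six comparisons. The SAP states no family-wise error.

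**Step 2: family-wise error of the rule as written.** Let P(x, y) be the two-sided Barnard p-value for x/18 vs y/18, and b(x; 18, p) the binomial probability. With one common rate p in all four arms,

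FWER(p) = 1 − Σ b(x₁)b(x₂)b(x₃)b(x₄) × Π over i<j of 1{P(xᵢ, xⱼ) > 0.05},

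summed over all outcomes of the four arms. The adjusted column replaces 0.05 by 0.05/6 = 0.0083.

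| Common rate | FWER, 0.05 per pair | FWER, 0.05/6 per pair |
|---|---|---|
| 2% | 0.2% | 0.0% |
| 5% | 3.4% | 0.0% |
| 8% | 10.5% | 0.1% |
| 10% | 14.8% | 0.2% |
| 20% | 18.8% | 2.6% |
| 30% | 19.0% | 3.9% |
| 40% | 18.6% | 3.5% |
| 50% | 15.2% | 2.8% |

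The results are symmetric above 50%. Over common rates of 10% to 90% the unadjusted range is 14.8% to 19.7%. For reference, six independent tests would give 1 − 0.95⁶ = 26.5%.

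**Step 3: the pooled 3M-052-AF arm.** After the second vaccination, section 9.4.1 pools Part A and Part B data for this adjuvant. That makes 10 + 20 = 30 enrolled and, assuming 10% missing, 27 evaluable. With 18, 18, 18 and 27, the unadjusted error is 14-19% at common rates of 10-90%, so the conclusion is unchanged.

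**Step 4: an example.** For 9/18 vs 15/18, Barnard's p = 0.038, which is a declared difference under the present rule. The Bonferroni-adjusted value is 6 × 0.038 = 0.23.

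**Step 5: what an adjusted reading costs in power.** By exact enumeration at 18 per arm:

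| True rates | Barnard at 0.05 | Barnard at 0.05/6 |
|---|---|---|
| 50% vs 95% | 91% | 72% |
| 50% vs 100% | 99.6% | 88% |

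Holm has at least the power of Bonferroni.

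**The case against.** **Magnitude is not strictly controlled either.** A reader might infer that magnitude is held to a family-wise 5% and rates are not. The SAP does not support that. Its second procedure uses nominal 95% intervals, section 9.4.1 also calls any two-sided p ≤ 0.05 significant, and nothing says which reading governs. Unadjusted testing of four arms on a normal outcome has a family-wise error of 20.3%, no better than the rate half. What stands is narrower: magnitude has an additional simultaneous reading and rates have none.

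**Unadjusted testing is a declared policy in a phase 1 trial.** Section 9 openly waives adjustment across endpoints, and section 8.3 warns that power for comparing rates is limited. This weighs against replacing the nominal rule. It does not settle the point, because the waiver does not mention arm pairs within one endpoint, and section 9.4.1 itself treats those pairs as a family for magnitude.

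**No stated decision hangs on the rate p-value.** Section 9.4.3 sets out comparisons of magnitude with pooled placebo, not pairwise rate tests. The ranking in Table 7 uses mean response. The neutralization table list in section 11.3.1 has no between-arm comparison table. All this is correct and limits the consequence, but the general rule of section 9.4.1 still applies to this endpoint.

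**The error depends on the true rates.** This also stands. Heterologous Tier 2 strains may show few responders, although the SAP gives no figure, and the error would then be small. The Arm 1 rates in Table 5 (10-50%) and the 50% vs 100% autologous example lie in the range where it is not.

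**Conclusion.** The point holds as a gap in reporting. One half of a primary endpoint has an adjusted and a nominal reading over six pairs, the other half only a nominal one, and the SAP does not say why. The chance of at least one false declared rate difference is about 15-20% per strain and timepoint. This assumes a common true rate of about 10-90% in all four arms and 18 evaluable per arm; pooling the 3M-052-AF arm barely changes it. Below about 8% it falls quickly.

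A reader might also want a single figure over Months 2.5 and 6.5 together. The chance over both visits is higher than at one, but its size depends on within-person correlation, which the SAP does not give, and on the arm sizes differing between visits because of the pooling. No combined figure is claimed here. Nor do the documents show that an adjuvant choice would turn on a rate p-value.

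**What to change.** In section 9.4.1, extend the two-procedure reporting to response rates. At each timepoint, give Holm- or Bonferroni-adjusted Barnard p-values over the six adjuvant pairs first and the nominal p-values second. Label any difference that is significant only at the nominal level as unadjusted.

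The change needs a few lines of SAP text and minor programming, with no new data and no change of design. The downside is that fewer rate differences will pass the adjusted reading, as the power figures above show. The nominal result stays visible, so no information is lost.

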A response is considered positive if the neutralization titer is above 10, the starting dilution, which is the limit of detection of the assay. Magnitude of response will be measured by the natural log of the ID50 and ID80 titer. An aggregate measure of response will be calculated as the area-under-the-magnitude-breadth curve (AUC-MB), which is equivalent to the mean log titer across all viruses in tier 2. If a titer is left censored, half the left censor limit will be used as the titer value.

For Part A of the study, neutralization titers will be measured on samples from the primary immunogenicity time point, week 10 (visit 9 – 2 weeks post 2nd vaccination) and as applicable, week 26 (visit 13 – 2 weeks post optional 2nd boost). Specimens from other time points may also be analyzed at the discretion of the PI, which may be contingent on the results of the primary immunogenicity time point. Those time points may include week 0 (visit 2 – baseline), week 2 (visit 6 – 2 weeks post 1st vaccination), and/or week 32 (visit 14 – 6 months post 2nd vaccination). For those who consented to the optional second boost, additional time points may include week 0 (visit 2 – baseline), week 2 (visit 6 – 2 weeks post 1st vaccination, week 24 (visit 11 – optional 2nd boost visit), week 52 (visit 15 – 6 months post optional 2nd vaccination), and/or week 78 (visit 16, 12 months post optional 2nd vaccination). Data from the two placebo groups in Part A (P1 and P2) will be pooled as Group C1.

For Part B of the study, neutralization titers will be measured on samples from the primary immunogenicity time point, week 10 (visit 9 – 2 weeks post 2nd vaccination) and week 26 (visit 13 – 2 weeks post 3rd vaccination). Specimens from other time points may also be analyzed at the discretion of the PI, which may be contingent on the results of the primary immunogenicity time point. Those time points may include week 0 (visit 2 – baseline), week 52 (visit 15 – 6 months post 3rd vaccination), and/or week 78 (visit 16, 12 months post optional 2nd vaccination). Data from the four placebo groups in Part B (P3, P4, P5, and P6) will be pooled as Group C2.

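### Rank-based magnitude comparisons carry two significance rules with no precedence, and with censored titers tied at one value the Hodges-Lehmann limit can sit at zero while the Wilcoxon test rejects

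*SAP*

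**What the plan says.** SAP 9.4.1 (General approach) says that the difference between arms at a timepoint "will be tested with a nonparametric Wilcoxon rank sum test if the data are not normally distributed". For that case, "If rank-based tests are used, then the tests will be inverted to construct Hodges-Lehmann point estimates", with "confidence intervals (CIs) about the differences in location centers of the 6 pair-wise comparisons of vaccine arms" at level 1 − 0.05/6.

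Two decision rules follow in the same section:

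- **Interval rule.** "Significance of the differences between pairs will be evaluated using two procedures, first based on whether the simultaneous 95% CIs exclude zero". The second procedure applies the same criterion to the interval without multiplicity adjustment.
- **P-value rule.** "All statistical tests will be 2-sided and will be considered statistically significant if" p ≤ 0.05.

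The section also offers a two-part test with a permutation p-value for readouts dichotomized into responder and non-responder. It applies if a mixture model is judged the best summary, and location differences are then estimated among positive responders only.

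SAP 11.3 puts the detection limit and positivity threshold at a titer of 10 and analyzes the natural log of the titer. It adds: "If a titer is left censored, half the left censor limit will be used as the titer value". Every censored titer therefore becomes 5. Neither section mentions ties, or an interval limit that equals zero.

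**The concern.** A Hodges-Lehmann interval from an inverted Wilcoxon test assumes that one arm's values equal the other's plus a constant. A block of identical values at ln 5 in both arms breaks that model. Every pair of non-responders, one from each arm, differs by exactly zero. At shift zero the Wilcoxon statistic counts each such pair as one half. At any shift just above zero, all of them count against the better arm. The statistic jumps at zero, and the interval limit can settle there even though the test at zero rejects.

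The magnitude part of Part B primary endpoint 2 (neutralization 2 weeks after the second and third vaccinations) is at stake. For one data set, the interval rule and the p-value rule can give opposite answers, and the plan does not say which one is reported.

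**Working it through.** **Inputs.** n = 18 per arm for analysis at Months 2.5 and 6.5 (SAP 8.3). Response-rate pairs come from the 80%-power column of Table 5, plus the 50% v 100% macaque scenario (SAP 8.3); they serve as scenarios only. Censored titers are 10/2 = 5 (SAP 11.3). There are six pairs, so the adjusted level is 0.05/6 = 0.0083.

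**1. The plan's own power figure.** Table 6 gives 81% (n = 18) and 78% (n = 17) for a 1.0 SD shift with a one-sided 0.025 Wilcoxon test. Simulation gives 80.0% and 78.3%, so the figures reproduce. They assume continuous normal data without ties, so they do not describe the interval rule applied to censored titers.

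**2. One data set by hand: 0/18 v 10/18 responders.** This result does not depend on the responders' titers.

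- Pairs: 18 × 18 = 324. Tied pairs: 18 × 8 = 144. Pairs favoring the better arm: 18 × 10 = 180.
- U = 180 + 144/2 = 252. Its null mean is 162, so the difference is 90.
- Var(U) = (mn/12)[(N + 1) − Σ(t³ − t)/(N(N − 1))]. One tied group of 26 gives 17,550/1,260 = 13.93, so Var = 27 × (37 − 13.93) = 623 and SD = 24.96.
- At shift zero, z = 90/24.96 = 3.61. With continuity correction, p = 0.0003.
- Just above zero, U = 180 and the difference is 18. The tied groups are now 18 and 8, giving 6,318/1,260 = 5.01, Var = 27 × 31.99 = 864, SD = 29.4 and z = 0.61.
- Order-statistic lower limit: rank 162 − 1.96 × √(324 × 37/12) = 162 − 1.96 × 31.61 ≈ 100. The smallest 144 differences are all zero, so the 95% limit is exactly 0. The 99.17% limit uses a lower rank and is also 0.

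**3. Further data sets** (responder titers assumed lognormal, geometric mean 60, log-SD 1, truncated above 10):

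| Responders of 18 | Wilcoxon p | 95% order-statistic interval (log scale) |
|---|---|---|
| 2 v 10 | 0.007 | (0, 2.16) |
| 2 v 12 | 0.0013 | (0, 2.43) |
| 5 v 15 | 0.003 | (0.34, 2.53) |
| 9 v 18 | 0.010 | (0.38, 2.33) |

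The limit leaves zero once few pairs are tied.

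**4. How often the rules disagree.** Simulation with 18 v 18, nominal 95%, order-statistic interval. Each cell is the percentage with Wilcoxon p ≤ 0.05 v the percentage with the interval excluding zero.

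| Response rates | Latent normal titers, censored at the limit | Equal titer distribution among responders |
|---|---|---|
| 10% v 58% | 92 v 12 | 88 v 11 |
| 20% v 71% | 94 v 43 | 86 v 32 |
| 30% v 81% | 96 v 71 | 81 v 49 |
| 40% v 89% | 98 v 92 | 77 v 60 |
| 50% v 95% | essentially no loss | 68 v 61 |
| 50% v 100% | essentially no loss | 77 v 77 |

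At 0.05/6, the equal-titer model gives 65 v 4 at 10% v 58%, 62 v 14 at 20% v 71%, and 50 v 51 at 50% v 100%.

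**5. In R.** With `wilcox.test(conf.int=TRUE)`, the 2 v 10 data set returns a lower limit of +0.00007 at 95% and −0.00004 at 99.17%. In 3,000 runs at 10% v 58%, 77% rejected with a limit within 0.001 of zero: 65% just above it and 12% at or below it.

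**The case against.** The strongest reply is that strict inversion makes no error. The set of shifts not rejected excludes zero exactly when the test rejects at zero. In the 0 v 10 example z is 3.61 at zero, so the set is open there. The order-statistic formula is one implementation, its variance carries no tie correction, and 9.4.1 does not name it. In R, which the plan allows alongside SAS, unrounded limits under the latent normal model exclude zero in 80% of runs at 10% v 58% (Wilcoxon 92%), 91% at 20% v 71% (94%) and 95% at 30% v 81% (96%). This stands, and it rules out saying that the plan necessarily loses these differences. It does not rescue the rule. Those limits lie at numerical error from zero, so rounding or another routine can reverse the verdict.

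Second, 9.4.1 also contains the p ≤ 0.05 rule and the two-part route, whose location estimates use responders only and so avoid the censored ties. Both are there. However, the plan ranks neither above the interval rule, gives no criterion for choosing the two-part route, and does not commit titers to it. Section 11.3.1 summarizes titers among all participants as well as among responders, so an all-participant comparison is a natural reading.

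Third, the response-rate part of the same endpoint is tested separately by Barnard's test. It was significant in 96%, 88% and 70% of the order-statistic conflicts at the first three rate pairs. Most such adjuvant differences would therefore still surface as response-rate differences. That limits the consequence, but leaves the magnitude conclusion unsettled.

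**Conclusion.** The point holds as a conflict between two rules, confined to rank-based comparisons of the six vaccine-arm pairs with many non-responders in both arms. There the interval rule can report no magnitude difference when the Wilcoxon test rejects, or give an answer that depends on the software. With the order-statistic interval the gap is large at 10% v 58% through 30% v 81%. It is small at 40% v 89% under latent normal titers and larger if responders' titers are alike in both arms. It is absent at 50% v 100%.

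A reader might infer three stronger things that the document does not support:

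- **That real differences are always declared non-significant.** This depends on which rule is applied, how the interval is computed, and how many pairs tie.
- **That comparisons with pooled placebo are affected in the same way.** The Hodges-Lehmann sentence names only the six vaccine-arm pairs, and 9.4.3 compares mean magnitude with placebo.
- **That the rules agree only when nearly everyone in the lower arm responds.** The 50% v 100% results show otherwise.

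The percentages rest on assumed titer distributions, which the SAP does not give. The mechanism in the 0 v 10 example does not depend on them.

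**What to change.** In 9.4.1, for rank-based comparisons of the six vaccine-arm pairs, state that significance comes from the tie-corrected or permutation Wilcoxon p-value: at 0.05 for the nominal procedure and at 0.05/6 for the adjusted one. State that the Hodges-Lehmann interval is descriptive and does not decide significance.

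For endpoints with values at the detection limit, name the effect measure. This can be the Mann-Whitney probability P(X > Y) + 0.5 P(X = Y) with its interval, or a geometric mean ratio from a left-censored normal model. The SAP already cites a mixed model for censored data.

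The cost is a few sentences and a few lines of code, with no new data. The small downside is that the effect measure for censored assays is no longer a location shift.

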9.4.3 Primary analyses of neutralization data

The primary measure of antibody neutralization is the response to the response to the vaccine-matched BG505.T332N isolate. As well, responses to a single highly neutralization-sensitive Tier 1 virus (MW965.26) will be assessed. The mean magnitude of the response to the vaccine-matched isolate will be estimated for each arm and compared to the pooled placebo group. As well, the ratio of the response to the vaccine-matched antigen, relative to that to the neutralization-sensitive isolate, will be estimated for each arm.

If a Tier 2 panel of viral isolates is used to assess the breadth of neutralizing antibody responses, the area-under-the-magnitude-breadth curve (AUC-MB) to a global panel of viral isolates [11] will be computed for each participant with evaluable neutralization data, as described in [12]. 95% CIs about the four differences in mean AUC-MB for each vaccine regimen versus the pooled placebo groups (vaccine – placebo), will be calculated.

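### SAP 9.4.1: the Dunnett intervals against pooled placebo assume one common variance, which the half-limit titer rule in 11.3 can make untrue by construction; the resulting width error depends on how the other adjuvant arms spread

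*SAP*

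**What the plan says.** Section 9.4.1 chooses the method by the shape of the data: a "nonparametric Wilcoxon rank sum test if the data are not normally distributed", and a two-sample t-test if they appear normal.

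- **Actual-value route.** Only if this route is taken, Dunnett's "procedure will be used to construct simultaneous confidence intervals about the pairs of mean differences for the many-to-one comparisons" of each vaccine arm with pooled placebo. For vaccine pairs, "the Tukey procedure [3] will be used". A transformation may be applied to better "satisfy assumptions of symmetry and homoscedasticity (constant variance"). No unequal-variance version is offered.
- **Rank route.** Hodges-Lehmann estimates and intervals are specified only "about the differences in location centers of the 6 pair-wise comparisons of vaccine arms". None is specified against placebo.
- **Significance.** It is read twice, from the simultaneous and from the nominal 95% intervals.

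Section 9.4.3 creates the need for a placebo contrast: "The mean magnitude of the response to the vaccine-matched isolate will be estimated for each arm and compared to the pooled placebo group". It also asks for 95% intervals on four vaccine-minus-placebo differences in mean AUC-MB if a Tier 2 panel is used. Section 11.3 analyses titers on the natural log scale with a detection limit of 10, and adds: "If a titer is left censored, half the left censor limit will be used as the titer value".

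**The concern.** Taken together, these rules conflict. A placebo recipient with no detectable activity gets exactly ln 5, and if all eight are undetectable the placebo group has no variance. No transformation gives variance to a constant, so the only remedy that 9.4.1 offers cannot work here. A pooled-variance method then charges the placebo mean, based on eight people, with sampling error that it does not have. It also gives every vaccine arm the average spread of all arms instead of its own.

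At stake are the error bars on the primary neutralization measure in Part B. An adjuvant's interval against placebo would widen or narrow according to how variable the other adjuvants' responses are, which says nothing about the adjuvant in question.

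**Working it through.** The SAP states no width or power for vaccine against placebo, so there is no figure to reproduce directly. As a check on the design inputs, Table 6 (vaccine against vaccine, n = 18) simulates to 62/72/80/87/92/96%, against the stated 63/71/81/85/92/97%.

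**Inputs.** Four vaccine arms with n = 18 for analysis at Months 2.5 and 6.5 (8.3). Pooled placebo n = 8 in Part B (9.4.1). Censored titer 10/2 = 5 (11.3). Two-sided 0.05. Assumed: placebo SD 0, and vaccine SDs as given below, because the SAP gives no titer SD.

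**Formulas**
- Residual df = 4×18 + 8 − 5 = 75.
- Pooled variance = Σ(nᵢ − 1)sᵢ²/75.
- Dunnett SE = √[pooled variance × (1/18 + 1/8)].
- Unequal-variance SE = √(sᵢ²/18 + s₀²/8).

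**Equal vaccine SD (1), placebo SD 0**
- Pooled variance = 4×17/75 = 0.907.
- Dunnett SE = √0.907 × √0.1806 = 0.952 × 0.425 = 0.405.
- Unequal-variance SE = 1/√18 = 0.236. Ratio 1.72.
- Simultaneous half-widths: 2.43 × 0.405 = 0.98 for Dunnett; 2.78 × 0.236 = 0.66 for Sidak over four contrasts on 17 df. Ratio 1.50.
- Nominal half-widths: 1.99 × 0.405 = 0.81 against 2.11 × 0.236 = 0.50. Ratio 1.62.

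**Placebo not constant.** With placebo SD 0.25 or 0.5 of the vaccine SD, the SE ratio is 0.406/0.252 = 1.61 or 0.410/0.295 = 1.39.

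**Pooled 3M-052-AF arm after dose 2.** Groups 2 and 4 give 10 + 20 = 30, or 27 after 10% missing. Pooled variance = (26 + 51)/84 = 0.917. SE = √0.917 × √(1/27 + 1/8) = 0.385, against 1/√27 = 0.192. Ratio 2.00.

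**Unequal vaccine SDs, placebo SD 0**

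| Vaccine SDs | Pooled variance | Dunnett SE | SE ratio | Width ratio |
|---|---|---|---|---|
| 1, 0, 0, 0 | 17/75 = 0.227 | 0.202 | 0.86 (first arm) | 0.75 |
| 1, 0.3, 0.3, 0.3 | 17×1.27/75 = 0.288 | 0.228 | 0.97 first; 3.22 others | 0.85 first; 2.82 others |
| 1, 0.75, 0.5, 0.25 | 0.425 | 0.277 | 1.18 / 1.57 / 2.35 / 4.70 | 1.03 / 1.37 / 2.05 / 4.10 |

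**Effect on detection.** Simulated share of trials in which the interval against placebo excludes zero. Non-responders are fixed at ln 5 and responders are log-normal with median titer 30 and log SD 0.8, both assumed.

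| Responder rates | Dunnett | Nominal pooled | Unequal-variance Sidak |
|---|---|---|---|
| 50% in all arms | 0.30 | 0.60 | 0.88 |
| 80% in all arms | 0.98 | 1.00 | 1.00 |
| 50% in one arm, 2% in the other three (the 50% arm) | 0.96 | 0.99 | 0.88 |

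At 35% in all arms (median titer 50, log SD 0.9) Dunnett excludes zero in 8% of trials, against 48% for a Welch interval with Bonferroni. The first and third rows concern an arm with the same data; only the other arms differ.

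**The normality rule.** About 97% of simulated 18-person arms with 50% responders fail Shapiro-Wilk. At 80-100% responders, about 67-96% pass under the median-30 assumption, and fewer if responder titers lie further above the floor. A rerun at 80-100% responders kept the Dunnett interval about 1.5 times the unequal-variance width.

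**The case against.** Dunnett is conditional. Eight identical placebo values, or a vaccine arm half at the floor, do not look normal, so the plan's own rule would usually send such data to Wilcoxon. Unadjusted, that test detects a 50%-responder arm in about 75-77% of trials. Section 9.4.1 also has a two-part test for mixtures of responders and non-responders, with a permutation p-value. This largely stands: the 0.30 against 0.88 contrast describes a case that would seldom reach Dunnett. It does not dispose of the point. Arms with high response rates can look normal and reach Dunnett, and the rank route supplies no interval against placebo.

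Three stronger readings are tempting, and the document does not support them:

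- **Intervals always 1.7 times too wide.** That figure is a ratio of standard errors under equal vaccine spread and a constant placebo. The width ratio is about 1.5, and it drops below 1 for a lone responding arm.
- **Real responses go undetected.** Response is called per participant at a titer above 10 and reported as rates with score intervals, neither of which uses Dunnett. The nominal interval is a second criterion.
- **Tukey breaches its level for individual vaccine pairs.** Tukey shares the equal-variance assumption, but it promises familywise coverage and the SAP states no pairwise level.

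Zero placebo variance is also assumed; 9.4.1 acknowledges that controls can be false positives.

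**Conclusion.** The point holds in a limited form. On the actual-value route, the only interval specified against placebo rests on a variance assumption that the censoring rule defeats whenever placebo stays at the floor.

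- **Similar spread across vaccine arms:** simultaneous intervals are about 1.5 times too wide and nominal ones about 1.6 times.
- **One arm at about 50% responders, the others near the floor:** the responding arm's interval is about 0.8 times the unequal-variance width. The others get intervals several times that width, although no normal-theory interval covers well in such low-response arms.
- **Consequence:** a large effect on significance is confined to about 35-50% responders with similar spread in all arms, where Wilcoxon would usually be chosen. At 80% or more responders the loss is of precision.

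The sizes rest on n = 18 and n = 8, which the SAP gives, and on placebo SD and titer distributions, which it does not. A placebo SD of half the vaccine SD lowers the SE ratio from 1.72 to 1.39.

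**What to change.** In 9.4.1, for vaccine against pooled placebo, replace equal-variance Dunnett with Welch/Satterthwaite intervals, adjusted over the four contrasts by Dunnett T3 or by Bonferroni or Sidak. State that where an arm has few responders (about 20% or less), inference rests on the two-part permutation test already in 9.4.1 and on the response rates, because the Welch interval also covers poorly there. State which interval, if any, is reported against placebo on the rank route. Games-Howell in place of Tukey for the vaccine pairs is optional.

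The cost is a few lines of SAP text and a different function call, with no new data and no design change. Degrees of freedom fall from 75 to about 17, which the 0.66 SD half-width above already includes.
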